### **APPENDIX 13. SUBJECT GLOBAL SATISFACTION WITH HAIR QUALITY FOR AT/AU (SGSHQ-AT/AU)**

**Instructions:** Please mark an “X” in the box (☐) that best describes your satisfaction with your scalp hair quality (such as its color, texture, and thickness) right now. Please select the one response that best represents your answer.

1. How satisfied or dissatisfied are you with your **scalp** hair quality right now?

- Extremely satisfied**
- Moderately satisfied**
- A little satisfied**
- Neither satisfied or dissatisfied**
- A little dissatisfied**
- Moderately dissatisfied**
- Extremely dissatisfied**

## APPENDIX 14. SUBJECT GLOBAL IMPRESSION OF CHANGE (SGIC)

(Please mark an "X" in the box (☐):

1. Compared to your hair loss at the beginning of the study [before starting study medication], your alopecia is?

- 1=Very much improved since starting study medication
- 2=Much improved
- 3=A little improved
- 4=No change since starting study medication
- 5=A little worse
- 6= Much worse
- 7=Very much worse since starting study medication

## APPENDIX 15. STUDY MEDICATION INSTRUCTION SHEET

### General Instructions:

1. Each month during the treatment phase of the study, the site staff will provide you with a one-month supply of study medication (with a few extra doses in case of spillage, loss or a missed appointment).
2. Do not take the study medication on an empty stomach. Food improves how much drug is absorbed and how much drug reaches your blood, which will give the drug the best chance of reaching your scalp.
3. You will drink one bottle of study medication two times a day with a meal (approximately 8 to 12 hours between doses).
4. Make sure the cap is tightly secured and gently shake the study medication before taking a dose.
5. Swallow all the study medication in the bottle.
6. Add water to the study medication bottle and drink the liquid, followed by a large glass of water.
7. Do not change your dose without talking to the study doctor.
8. Avoid excessive natural or artificial ultraviolet radiation (e.g., sunlight, tanning beds) and use sunscreen, if excessive sun exposure cannot be avoided.
9. Remember to bring your compliance sheet, study medication bottles, both used and unused, to each study visit.

### Missed Doses

If you miss a dose of this study medication, take the dose as soon as possible. However, if it is almost time for your next dose, skip the missed dose, and go back to your regular dosing schedule. Tell the study staff about any missed doses at your next study visit.

### Storage

Store the study medication in the original bottle at room temperature, away from heat, moisture, and direct light. Do not refrigerate or freeze. Keep out of reach of children.

---

## TABLE OF CONTENTS

### GLOSSARY OF ABBREVIATIONS

Abbreviation	Term
AA	Alopecia Areata
AAP	Patchy Alopecia Areata
AFHA	Alopecia Facial Hair Appearance Assessment
AT	Alopecia Totalis
AU	Alopecia Universalis
AE	Adverse Event
AIA-PRO	Alopecia Impact Assessment-Patient Reported Outcome
ALODEX	Alopecia Density and Extent Score
BID	Twice daily
CBC	Complete Blood Count
CI	Confidence Interval
ClinRO	Clinician Reported Outcome
CRF	Case Report Form
CR	Clinician Rating
DLQI	Dermatology Life Quality Index
ECG	Electrocardiogram
eCRF	Electronic Case Report Form
ICF	Informed Consent Form
ITT	Intent-to-Treat
LOCF	Last Observation Carried Forward
LS Mean	Least Squares Mean
MedDRA	Medical Dictionary for Regulatory Activities
MMRM	Mixed Effect for Repeated Measures
mL	Milliliter
msec	Millisecond
NSHA	Non-Scalp Hair Loss Assessment
PE	Physical Examination
PhGIC	Physician Global Impression of Change
PhGIS	Physicians Global Impression of Severity
PP	Per- protocol
PRO	Patient-Reported Outcome
SAE	Serious Adverse Event
SALT	Severity of Alopecia Tool
SAP	Statistical Analysis Plan
Scalp-ClinRO	Scalp-ClinRO for AAP 
Scalp-PRO	Scalp-PRO for AAP 
SGIC	Subject Global Impression of Change
SGIS	Subject Global Impression of Severity
SGITS	Subject Global Impression of Treatment Satisfaction
SGSHQ	Subject Global Satisfaction with Hair Quality

SR	Subject Rating
TEAE	Treatment Emergent Adverse Events
UPT	Urine Pregnancy Test
WHO	World Health Organization
WOCBP	Women of Child Bearing Potential

This assessment is named Alopecia Scalp Appearance Assessment-Clinician Rating (ASAA-CR) in the protocol.

Subjects with Patchy AA complete Item 1 and Item 2 (target patch and whole scalp assessment). Subjects with Alopecia Totalis or Alopecia Universalis complete the assessment for the whole scalp only.

This assessment is named Alopecia Scalp Appearance Assessment-Subject Rating (ASAA-SR) in the protocol. Subjects with Patchy AA complete Item 1 and Item 2 (target patch and whole scalp assessment). Subjects with Alopecia Totalis or Alopecia Universalis complete the assessment for the whole scalp only.

## 1. INTRODUCTION

This document describes the statistical methods and data presentations to be used in the summary and analysis of data from Protocol ATI-501-AUAT-201. Background information is provided for the overall study design and objectives. The reader is referred to the study protocol and case report forms (CRFs) for details of study conduct and data collection.

The scope of this document excludes the evaluation of the psychometric properties of the newly developed patient-reported and clinician-reported outcome (PRO and ClinRO) questionnaires. Additionally, the generation of score interpretation estimates for the clinical outcome assessments to guide the definition of responders in pivotal trials is also not within the scope of this SAP.

### 1.1. STUDY OVERVIEW

ATI-501-AUAT-201 is a Phase 2, multicenter, randomized, double-blind study designed to evaluate the safety, tolerability and efficacy of ATI-501 Oral Suspension in subjects with alopecia areata (AA), alopecia universalis (AU), or alopecia totalis (AT). Subjects will be required to have a clinical diagnosis of stable AA, AU, or AT with at least 30% up to 100% total scalp hair loss for a duration of at least 6 months up to and including 12 years.

#### **Treatment Assignment:**

A total of approximately 95 subjects will be randomized in a 1:1:1:1 ratio:

- Placebo Oral Suspension, twice daily (BID) for 24 weeks (6 months)
- ATI-501 Oral Suspension, 400 mg, BID for 24 weeks (6 months)
- ATI-501 Oral Suspension, 600 mg, BID for 24 weeks (6 months)
- ATI-501 Oral Suspension, 800 mg, BID for 24 weeks (6 months)

During the screening period, subjects will be assessed for eligibility into the study. Subjects will receive ATI-501 Oral Suspension, 400 mg, 600 mg, or 800 mg or Placebo Oral Suspension twice-daily for up to 24 weeks. Assessment of response to treatment will be performed at Week 4 (Visit 4), Week 8 (Visit 5), Week 12 (Visit 6), Week 16 (Visit 7), Week 20 (Visit 8), Week 24 (Visit 9), and post-treatment (Visit 10). Safety and tolerability will be evaluated at each study visit by assessment of adverse events (AEs), clinical lab tests, vital signs, and at select visits, ECGs. The primary analysis will be conducted after all subjects complete Visit 9 or Visit 10.

Subjects who complete Visit 9 (Week 24) will be eligible to enter a 28-week open-label study ATI-502-AA-203. Subjects who decline or are not eligible for ATI-502-AA-203 should be seen for the Visit 10 (Post-treatment) assessments.

**1.2. SCHEDULE OF ASSESSMENTS**

		Screening	Baseline	Treatment						Post-Treatment	
		Visit 1	Visit 2	Visit 3 	Visit 4	Visit 5	Visit 6	Visit 7	Visit 8	Visit 9 (ET)	Visit 10 
	Week		0	2	4	8	12	16	20	24	28
	Treatment Day	-30 to 0	1	15	29	57	85	113	141	169	197
	Treatment window (days)	N/A	N/A	±3	±3	±3	±3	±3	±3	±3	±3
	Informed consent 	X									
	Inclusion/exclusion criteria	X	X								
	Physical exam 	X								X	
	Demographics & medical history	X									
	Alopecia Areata History	X									
	Vital signs 	X	X	X	X	X	X	X	X	X	X
	Clinical Complete Blood Count (CBC), Chemistry, Virology, Serum Pregnancy, Urinalysis 	X 	X	X	X	X	X	X	X	X	X
	Blood for PK (Select Sites Only) 		X (Pre-dose)		X		X			X	
	Urine pregnancy test 	X	X		X	X	X	X	X	X	X
	ECG	X		X						X	
Subject 	Target Patch identification (Patchy AA Subjects Only)		X								
	Scalp-PRO Target Patch, Whole Scalp 		X	X			X			X	X
	Alopecia Facial Hair Appearance Assessment (AFHA: SR)		X	X			X			X	X
	Subject Global Impression of Severity (SGIS-AAP (patchy alopecia areata) or SGISAT/AU)		X	X			X			X	X
	Alopecia Impact Assessment (AIA): Subject Rating		X	X			X			X	X
	Subject Global Impression of Change (SGIC)									X	
	Subject Global Impression Treatment Satisfaction (SGITSAAP or SGITSAT/AU) 						X			X	X
	Subject Global Satisfaction with Hair Quality (SGSHQAAP or SGSHQAT/AU)		X	X			X			X	X
	DLQI 		X	X			X			X	X

		Screening	Baseline	Treatment						Post-Treatment	
		Visit 1	Visit 2	Visit 3 	Visit 4	Visit 5	Visit 6	Visit 7	Visit 8	Visit 9 (ET)	Visit 10 
Week			0	2	4	8	12	16	20	24	28
Treatment Day		-30 to 0	1	15	29	57	85	113	141	169	197
Treatment window (days)		N/A	N/A	±3	±3	±3	±3	±3	±3	±3	±3
Investigator 	Scalp-ClinRO Target Patch, Whole Scalp 		X	X			X			X	X
	Alopecia Facial Hair Appearance Assessment (AFHA: CR)		X	X			X			X	X
	Non-Scalp Hair Loss Assessment (NSHA)		X	X			X			X	X
	Physician Global Impression of Severity (PhGIS-AAP or PhGIS-AT/AU)		X	X			X			X	X
	Physician Global Impression of Change (PhGIC)									X	
	Hair Quality Assessment (Patchy AA Subjects Only)		X				X			X	X
	SALT Score (prior to ALODEX) 	X	X	X	X	X	X	X	X	X	X
	ALODEX Score (after SALT) 	X	X	X	X	X	X	X	X	X	X
Vellus and Indeterminate Hair Assessment	X	X	X	X	X	X	X	X	X	X	
Photography (complete scalp)			X		X	X	X	X	X	X	
Subject randomization			X								
Subject instructions 			X		X	X	X	X	X	X	
Dispense study medication 			X	X 	X	X	X	X	X		
Collect study medication and assess compliance 			X	X	X	X	X	X	X	X	X
Concomitant therapies			X	X	X	X	X	X	X	X	X
Adverse events			X	X	X	X	X	X	X	X	X

Abbreviations: CR= Clinician Rating; ET= Early termination Visit; SR= Subject Rating

 Efficacy assessments completed at Visit 3 are to test the reliability of the clinician and patient reported outcome tools.

 A written, signed informed consent form (ICF) must be obtained from each subject prior to performing any study related procedure (i.e., prior to performing vital signs, standardized photography, biopsies, clinical laboratory sampling or urine pregnancy tests).

 A physical exam includes: general appearance, examination of head, eyes, ears, nose and throat, respiratory, cardiovascular, abdominal, neurological, musculoskeletal, extremities, lymphatic and skin assessment (other than AA).

 Vitals signs include: oral or ear temperature, blood pressure, heart rate, respiration rate (height and weight at Screening only).

 Clinical laboratory non-fasting sampling includes: CBC, Chemistry with lipids, Urinalysis. Quantiferon Gold, Human Immunodeficiency Virus (HIV), Hepatitis B and C, TIBC, Serum Iron, Serum Ferritin, T3, free T4, TSH and Serum Pregnancy should be done at screening visit only.

 At Select sites: A single 4.5 milliliters (mL) sodium citrate vacutainer should be drawn at Visit 2 (predose) and Visits 4, 6, and 9, 12 hours (± 30 minutes) after the prior evening dose. Subjects participating in the PK analysis should be called the day prior to Visit 4, 6, and 9 to remind them to take their evening dose approximately 11 hours prior to the visit time and to document the time of the evening dose.

 Subjects who are women of child-bearing potential (WOCBP) should have a urine pregnancy test (UPT) performed early in the screening procedures (following informed consent) which shows negative results in order to avoid the continuation of what would then be unnecessary screening testing. Subjects who are WOCBP must also have a negative serum pregnancy test result from Screening (Visit 1) to continue in the study, and a negative UPT at Baseline (Visit 2) prior to randomization. UPTs in WOCBP must also be obtained at Visits 4, 5, 6, 7, 8, 9 and 10 and must be negative for the subject to continue in the study.

 The subject should perform assessments prior to the Investigator assessments. The investigator may assist the subject in locating a Target Patch.

 Subjects with 30% to 95% scalp hair loss will identify the most bothersome patchy area at Baseline (Visit 2). A score of “no hair” or “a little hair” in the target patch is required. For subjects with AU or AT, the target patch identification at Baseline (Visit 2) will be recorded as “Not Applicable” in the source document and eCRF.

 The study staff should remind the subject that this question is in relation to the satisfaction with the result of the hair regrowth.

 The study staff should remind the subject that the questions are in relation to hair loss and not skin.

 Investigator assessments should be performed after the Subject Assessments.

 In subjects with patchy AA, the assessment of hair quality will be performed at the edge of the target patch. For subjects with AU/AT, the assessment of hair quality will be recorded as Not Applicable in the source document and eCRF. At Baseline (Visit 2), the assessment should be determined prior to the first dose of study medication.

 SALT score must be determined prior to ALODEX using device provided.

 ALODEX score determined after SALT score using device provided.

 The study staff must instruct the subject to dose study medication according to the instructions in Appendix 15.

 Staff should review the usage based on the number of used and unused bottles and counsel the subject as necessary.

 At Visit 3, the subject’s Month 1 drug supply carton should be reviewed by site staff as part of compliance activities and then released back to the subject for continued use.

 Subjects who complete study visits through Visit 9 will have the option to roll over into an open-label study ATI-502-AA-203. Subjects who withdraw consent or meet study medication discontinuation criteria (Section 3.4.1.2) on study ATI-501-AUAT-201 will not be eligible for roll-over to study ATI-502-AA-203. Subjects who complete the assessments for Visit 9 and then meet study ATI-502-AA-203 entry criteria and provide written consent will skip post-treatment Visit 10. Subjects who are not eligible for ATI-502-AA-203 or who decline to participate should return for the final Visit 10 assessments.

## 2. OBJECTIVES

### **Primary Objective:**

The primary objective is to assess the safety, tolerability and efficacy of ATI-501 Oral Suspension, 400 mg, 600 mg, or 800 mg compared to Placebo Oral Suspension in subjects with AA, AU, or AT.

### **Secondary Objective:**

The secondary objectives are as follows:

- To evaluate the psychometric performance of the key clinical outcome assessments questionnaires with respect to reliability, construct-related validity, and sensitivity to change. This objective is not within the scope of the SAP.
- To generate score interpretation estimates for the clinical outcome assessments to guide the definition of responders in pivotal trials. This objective is not within the scope of the SAP.
- To assess the concentration level of ATI-502 in the blood at trough.

### 3. EFFICACY AND SAFETY ASSESSMENTS

Efficacy assessments include the following scores and/or scales (Note: Target Patch and Entire Scalp assessments are performed for AAP subjects. Only Entire Scalp assessments are performed for AT/AU subjects):

- Severity Alopecia Tool (SALT) Score
- Alopecia Density and Extent Score (ALODEX)
- Item 1 and Item 2 Scalp-ClinRO for AAP (Scalp-AAP-ClinRO), referred to as Alopecia Scalp Appearance Assessment (ASAA-AAP:CR) in the protocol
- Scalp-ClinRO for AT/AU (Scalp-AT/AU-ClinRO), referred to as Alopecia Scalp Appearance Assessment (ASAA-AT/AU:CR) in the protocol
- Item 1 and Item 2 Scalp-PRO for AAP (Scalp-AAP-PRO), referred to as Alopecia Scalp Appearance Assessment (ASAA-AAP:SR) in the protocol
- Scalp-PRO for AT/AU (Scalp-AT/AU-PRO), referred to as Alopecia Scalp Appearance Assessment (ASAA-AT/AU:SR) in the protocol
- Physician Global Impression of Severity (PhGIS-AAP or PhGIS-AT/AU)
- Alopecia Facial Hair Appearance Assessment (AFHA-PRO and AFHA-ClinRO)
- Subject Global Impression of Severity (SGIS-AAP or SGIS-AT/AU)
- Alopecia Impact Assessment (AIA) – Subject Rating
- Subject Global Impression of Treatment Satisfaction (SGITS-AAP or SGITS-AT/AU)
- Subject Global Satisfaction with Hair Quality (SGSHQ-AAP or SGSHG-AT/AU)
- Dermatology Life Quality Index (DLQI) total score
- Physician Global Impression of Change (PhGIC)
- Subject Global Impression of Change (SGIC)
- Hair Quality Assessment (Hair Pull Test, AAP subjects only)
- Vellus and Indeterminate scalp hair
- Non-scalp hair assessments (body and nasal hair) (NSHA)

Safety assessments include:

- Adverse events
- Clinical laboratory tests (hematology, clinical chemistry, and urinalysis)
- Vital sign measurements (systolic and diastolic blood pressure, respiration rate, heart rate, and temperature)
- Electrocardiograms (ECGs)

## **4. GENERAL STATISTICAL CONSIDERATIONS**

### **4.1. SAMPLE SIZE AND POWER**

The planned sample size is 95 enrolled subjects with approximately 45 subjects enrolled with AT or AU. It is assumed that the proportion of subjects who achieve at least a 50% reduction in hair loss (SALT50) for the pooled 600mg and 800mg treatment groups will be at least 32%, and the SALT50 for the pooled placebo and 400mg treatment groups will be at most 6%. Assuming a 10% dropout rate, this results in >80% power for the SALT50 analysis. Because the primary efficacy analysis of mean percent change in hair loss using SALT scores is expected to be more sensitive than the SALT50 responder analysis, the power for the primary analysis is also expected to be no less than 84%.

### **4.2. RANDOMIZATION AND BLINDING**

Prior to the start of the study, Aclaris Therapeutics, Inc. or a designated third party will generate a list of randomization numbers that shall be transmitted to the assigned clinical packaging organization for study medication labeling. The randomization list will be stored with access limited to designated personnel for study medication labeling. The randomization list will be made available, as appropriate, to unblind the database.

In the treatment period, subjects will be assigned to 1 of the 4 treatment groups in a random manner and at a 1:1:1:1 ratio. At Baseline (Visit 2), an investigational center staff member will assign study medication to eligible subjects by selecting an appropriate Subject Kit. The staff member must select Subject Kits in chronological sequence and in an ascending numerical order starting with the lowest available Subject Kit number. No Subject Kit number may be omitted or reused. The Subject Kit number is the randomization number.

This study uses a double-blind design. The study medications are indistinguishable in appearance, as packaged and labeled.

### **4.3. HANDLING OF DATA**

#### **4.3.1. Strata and Covariates**

No stratified analyses are planned.

#### **4.3.2. Examination of Subject Subsets**

The baseline SALT score group ( $< 50$ ,  $\geq 50$ ) will be used for subset analyses. Additionally, duration of current episode ( $< 4$  years,  $\geq 4$  years) will be used for subset analyses. The details of the subset analyses are given in the statistical analysis section.

#### **4.3.3. Multiple Testing and Comparisons**

There are no planned adjustments for multiple comparisons.

#### 4.3.4. Missing Data and Outliers

For missing clinical assessments, the method of last observation carried forward (LOCF) will be used to impute values. The last non-missing value prior to the missing assessment will replace the missing values. For subjects who terminate early, missing assessment after the date of early termination will be replaced by the LOCF method.

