### **3. INVESTIGATIONAL PLAN**

#### **3.1. Overall Study Design**

This Phase 2, multicenter, randomized, double-blind study is designed to evaluate the safety, tolerability and efficacy of ATI-501 Oral Suspension in subjects with AA, AU or AT. Subjects will be required to have a clinical diagnosis of stable AA, AU or AT with 30% to 100% total scalp hair loss for a duration of at least 6 months up to and including 12 years (inclusive). Stable AA, AU or AT is defined as no areas of spontaneous terminal scalp hair growth.

During the screening period, subjects will be assessed for eligibility into the study. Subjects will receive ATI-501 Oral Suspension, 400 mg, 600 mg, or 800 mg or Placebo Oral Suspension twice-daily for up to 24 weeks. Assessment of response to treatment will be performed at Week 4, Week 8, Week 12, Week 16, Week 20, Week 24, and post-treatment Week 28. Safety and tolerability will be evaluated at each study visit by assessment of adverse events, clinical laboratory tests, and vital signs, and at select visits, ECGs.

Subjects who complete study visits through Visit 9 will have the option to roll over into an open-label study ATI-502-AA-203. Subjects who withdraw consent or meet study medication discontinuation criteria (Section 3.4.1.2) on study ATI-501-AUAT-201 will not be eligible for roll-over to study ATI-502-AA-203. Subjects who complete the assessments for Visit 9 and then meet study ATI-502-AA-203 entry criteria and provide written consent will skip post-treatment Visit 10. Subjects who are not eligible for ATI-502-AA-203 or who decline to participate should return for the final Visit 10 assessments.

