#### **3.3. Treatment Assignment**

Subjects will be randomized 1:1:1:1 to ATI-501 Oral Suspension 400 mg, 600 mg, 800 mg or Placebo Oral Suspension twice-daily for 24 weeks followed by a 4-week post-treatment follow up period.

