### 9.4.1. Primary Efficacy Analyses

The primary efficacy variable will be the percent change from Baseline (Visit 2) in the SALT score at Visit 9 (Week 24). Missing data for the primary endpoint will be imputed using Last Observation Carried Forward (LOCF) methodology. The analysis will be conducted on the percent change from baseline over time including all visits using a mixed effect model repeated measures (MMRM). The adjusted mean (LS Mean) for percent change from baseline in the SALT score at each visit, estimated from the MMRM, with the estimated standard error and 95% confidence interval (CI), will be presented in tabular and graphic format. The difference in the adjusted means between treatment groups and the associated 95% CI of the difference will be provided. No adjustment for multiplicity will be made. The model will include fixed effect terms for treatment, study visit, baseline SALT score group (<50, ≥50), and treatment by SALT group interaction. The primary analysis will be based on the Intent-to-Treat (ITT) population. Statistical significance for primary efficacy endpoint will be declared if at least one treatment group comparison at the Week 24 visit has a two-sided p-value less than or equal to 0.05.

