**Table 1: Visit Windows**

Nominal Visit	Target Study Day	Analysis Visit	Study Day Range
Screening	-30 to -1	Baseline	≤1
Day 1	1		
Week 2	15	Week 2	[12 – 22]
Week 4	29	Week 4	[23 – 42]
Week 8	57	Week 8	[43 – 70]
Week 12	85	Week 12	[71 – 98]
Week 16	113	Week 16	[99 – 126]
Week 20	141	Week 20	[127 – 154]
Week 24	169	Week 24	[155 – 182]

For the post-treatment visit 10, the analyses will be based on the nominal study visit as reported on the CRF.

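### Read literally, the unrestricted LOCF rule in SAP 4.3.4 would carry on-treatment Week 24 values into the off-treatment Week 28 visit for subjects who skip that visit by design

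*SAP*

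**What the plan says.** **Imputation.** SAP 4.3.4 reads: "For missing clinical assessments, the method of last observation carried forward (LOCF) will be used to impute values". The next sentence gives the mechanism: "The last non-missing value prior to the missing assessment will replace the missing values". The section adds that assessments missing after early termination are filled the same way. It sets no limit by visit, endpoint or treatment phase. Protocol 9.4.1 is narrower: "Missing data for the primary endpoint will be imputed using Last Observation Carried Forward (LOCF) methodology". That endpoint is defined at Week 24.

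**Design.** Protocol 3.3 describes dosing "twice-daily for 24 weeks followed by a 4-week post-treatment follow up period". Visit 10 at Week 28 is therefore off treatment. Under protocol 3.1, subjects who finish Visit 9, qualify for ATI-502-AA-203 and consent to it "will skip post-treatment Visit 10". Footnote 19 to the schedule in SAP 1.2 repeats this. Only those who decline or are ineligible return for Visit 10.

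**Analysis of Visit 10.** SAP Table 1 has analysis windows to Week 24 only, and adds: "For the post-treatment visit 10, the analyses will be based on the nominal study visit as reported on the CRF". Protocol 2.4 makes the by-visit secondary analyses conditional on data being available at the visit.

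**The concern.** A visit skipped because the design sends the subject elsewhere is not ordinary missing data. The value LOCF would supply is a score on ATI-501, while the visit it would fill is meant to show the subject off ATI-501. Any Week 28 figure built this way mixes observed off-treatment scores with copies of Week 24 and corresponds to no real population.

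Visit 10 is the only scheduled post-treatment assessment in this trial. A mean or proportion padded with Week 24 copies would make the effect look better maintained than it is. The two documents also point in different directions, so two programmers could produce different Week 28 tables from the same data, and the choice might be made after unblinding.

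**Working it through.** There is no stated figure to reproduce. The check is mainly textual, with an illustration of size.

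**Step 1: does the rule reach Visit 10?** Its wording covers any missing clinical assessment. SALT, ALODEX and the ordinal scales are all scheduled at Visit 10. A rollover subject has completed Visit 9, so the last earlier value is normally Week 24. Nothing in SAP 4.3.4 exempts the visit.

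**Step 2: does other text exempt it?**
- SAP Table 1 assigns Visit 10 records by the CRF visit label. This suggests observed data, because a skipped visit has no CRF record, but it does not mention imputation.
- SAP 6 bases by-visit percentages on subjects with a non-missing value. It does not say whether a carried-forward value counts as non-missing.
- Protocol 2.4 points to observed data and so conflicts with a literal reading of SAP 4.3.4.
- SAP 7 declares no departure from the protocol, although SAP 4.3.4 widens LOCF beyond the primary endpoint.

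**Step 3: which outputs are exposed?**
- SALT: an LOCF by-visit table (14.2.1.1) and an observed one (14.2.1.1a) are both planned.
- ALODEX: only the LOCF by-visit table (14.2.2.1) is listed.
- Responder tables (14.2.3.x) carry no LOCF or observed label, and SAP 6.2.8 plots the 50% regrowth proportions for SALT and ALODEX over time.
- SAP 6.2.5 runs Wilcoxon tests at each visit for the ordinal scales, including SGITS, which protocol 9.4.2 requires to be summarised at Week 28.
- The SAP's primary MMRM stops at Week 24. The SALT change, ALODEX and DLQI models use the same methods.

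**Step 4: how large could the distortion be?** Let r be the share of Week 24 completers who roll over and d the true loss from Week 24 to Week 28. Assume that rollover and non-rollover subjects would lose effect alike. Filled subjects contribute zero change, so:
- displayed loss = (1 − r) × d
- displayed responder rate = r × (Week 24 rate) + (1 − r) × (Week 28 rate)

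The documents give neither r nor d. The table assumes d = 20 percentage points of percent change, and a SALT50 rate that falls from 32% (the SAP 4.1 planning rate for the pooled 600 mg and 800 mg groups) to an assumed 16%. Observed n uses 95 subjects and 10% dropout from SAP 4.1: 95 × 0.9 = 85.5 completers, multiplied by (1 − r), then divided by 4 arms.

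| r (assumed) | Displayed loss when d = 20 | Displayed SALT50 rate (true 16%) | Observed Week 28 n | Per arm |
|---|---|---|---|---|
| 25% | 15 | 20% | 64 | 16 |
| 50% | 10 | 24% | 43 | 11 |
| 75% | 5 | 28% | 21 | 5 |
| 90% | 2 | 30.4% | 9 | 2 |

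For r = 50%: 0.5 × 20 = 10; 0.5 × 32% + 0.5 × 16% = 24%; 85.5 × 0.5 = 42.75, about 43. Early terminators, carried forward at both visits, also show zero change. Over all randomised subjects the r = 50% loss would then be 0.9 × 0.5 × 20 = 9.

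**The case against.** The strongest reply is that the SAP never says Week 28 is imputed. The CRF-based rule for Visit 10, the non-missing denominators and protocol 2.4 all lean towards observed data. SAP 6.2.2 presents SALT descriptives by analysis visit, and Table 1 defines those only to Week 24, so a Week 28 row in the LOCF tables is not certain. A visit the design tells a subject to skip is arguably not a missing assessment. This stands far enough to make the point conditional on a literal reading. It does not settle the matter, because none of these passages limits SAP 4.3.4.

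A reader might infer that filled Week 28 values enter the primary model, since protocol 9.4.1 describes an analysis "over time including all visits". The documents do not support that. Protocol LOCF covers only the Week 24 primary endpoint, and the SAP, which has the open-ended LOCF rule, ends its model at Week 24. Neither document both fills Week 28 and models it.

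A reader might also infer that loss of effect after stopping is hidden outright. For SALT it is not, because Table 14.2.1.1a gives observed values by visit.

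It is also fair that no objective or endpoint names durability after stopping, and that the illustration contains no trial information on r or d. Both limit the weight of the point. Finally, observed Visit 10 data come from a selected group, so the remedy does not recover durability in the randomised population.

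**Conclusion.** The point holds in limited form. As written, SAP 4.3.4 would place on-treatment values in an off-treatment visit for rollover subjects and would fill it for early terminators, in conflict with the protocol's narrower use of LOCF. The outputs at risk are any Week 28 results in the ALODEX by-visit summary, the responder proportions over time and the visit-wise Wilcoxon tests, including SGITS. The Week 24 primary result under the SAP does not change.

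The proportion of the loss concealed equals r. This assumes literal use of the rule, similar loss in rollover and non-rollover subjects, and an r that the documents do not give. The point should be settled before unblinding, but it does not threaten the trial's main conclusion.

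**What to change.** In SAP 4.3.4, state that LOCF applies only to scheduled visits up to and including Week 24 and never to Visit 10. State that Visit 10 is summarised as observed, with n by arm, labelled as the selected non-rollover subset and shown beside the same subjects' Week 24 values. Apply this to ALODEX, the responder proportions and the ordinal-scale tests.

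Separately, align the all-visits wording in protocol 9.4.1 with the SAP's Week 24 limit. This is a consistency edit.

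The cost is a short SAP addition and one protocol phrase. The downside is a smaller Week 28 n, about 11 per arm at r = 50% and 2 at r = 90% under the assumptions above. That n comes from subjects who declined or were ineligible, so the summary does not estimate durability in the whole randomised population and should say so.
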